1.2.2. Randomization and Blinding

Randomization will occur centrally using an interactive voice or web response system (IxRS) using central, stratified block randomization. Randomization will be done separately for Cohort 1 and Cohort 2 and will be stratified based on the following stratification factors:

- Baseline UUI episodes per day (≤ 3 vs. > 3), and
- Prior onabotulinumtoxinA use (naïve vs. prior use)

As mentioned in the previous section, subjects enrolled under the randomization scheme prior to protocol amendment 1 (Cohort 1a) will be considered onabotulinumtoxinA naïve when combined with Cohort 1b for analyses and summaries.

To maintain blinding of the treatment groups, neither the investigator/physician subinvestigator (injector) nor site personnel who are involved in evaluating or injecting the subject should prepare the study drug. An additional individual (eg, unblinded pharmacist or nurse) with no subject evaluation or treatment involvement must be identified at each investigative site to prepare the study drug and the PBS-20% flushing solution. The responsibility of this individual will be to properly prepare the injection syringes with the accurate randomized study drug as per the volumes indicated by the Sponsor. They will draw the study drug into the syringes to be injected and dilute as needed as per instructions in the study manual.

For the interim analysis(es), the subject and the investigator or delegate(s) who are involved in the treatment or clinical evaluation of the subjects will remain blinded to the treatment assignments. Limited personnel from the Sponsor will be unblinded (double-blind, sponsor-

open design). Sponsor personnel/designees who are directly involved with site interactions and communications (eg, study operations lead and site monitors) will remain blinded to subject level treatment assignment.

1.2.3. Statistical Hypotheses

The study has no formal statistical primary endpoint hypothesis. The intent is to estimate the treatment effect of each dose group relative to placebo. For the final analysis, the subjects receiving placebo from Cohort 1 and Cohort 2 will be pooled.

1.2.4. Sample Size Justification

For this exploratory study, the sample size was empirically chosen. With a total of 23 evaluable female subjects in each of the URO-902 treatment groups and 23 evaluable female subjects in the placebo group, this study would have approximately 55% power to detect a between-group difference of 1.8 episodes in the mean change from baseline to Week 12 in the number of UUI episodes per day between the URO-902 and placebo treatment groups (based on a 2-sample t-test with a 2-sided type I error rate of 0.05 and standard deviation [SD] of 2.86). Furthermore, the half-width of the confidence interval would be the following for different SD assumptions:

Table 1: Sample Size Determination Parameters

SD	N per Group	Half-Width of Confidence Interval	Lower Limit	Upper Limit
2.86	23	1.70	0.10	3.50
3.00	23	1.78	0.02	3.58
2.55	23	1.49	0.31	3.29

In order to account for subject attrition (approximately 10%), the sample size was increased to 26 subjects for each treatment group, amounting to a total of 78 randomized subjects required for exploratory efficacy analyses in both Cohort 1 (n = 39) and Cohort 2 (n = 39).

2. PLANNED ANALYSES

2.1. Interim Analysis

Two or more interim analyses may be conducted; when $\geq 50\%$ of subjects in Cohort 1, and/or when $\geq 50\%$ of subjects in Cohort 2 have completed at least 12 weeks of follow-up post-treatment administration (or prematurely exited the study prior to Week 12). Any interim analysis performed is for future planning purposes and no adjustment to the type I error will be made.

The planned interim analysis will be conducted to evaluate the objectives of the protocol at Week 12. These analyses will be performed after the completion of the following steps:

- All subjects in Cohorts 1 and 2 have completed Week 12 (or prematurely exited the study prior to Week 12).
- All required database cleaning activities have been completed and final database release and freeze has been declared by data management for all subjects to be included in the interim analysis.
- All criteria for unblinding the randomization code have been met.

Similar to the planned Week 12 interim analysis, a second planned interim analysis will be conducted after all subjects complete Week 24 (or prematurely exited the study prior to Week 24). This analysis will evaluate the objectives of the protocol at Week 24.

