1.2. Study Design

1.2.1. Overall Study Design

This is a multicenter, randomized, double-blind, placebo-controlled, single-treatment, 2-cohort, dose-escalation study.

URO-902 24 mg will be administered as intradetrusor injections to subjects in Cohort 1. An independent Data and Safety Monitoring Board (DSMB) will make the recommendation

regarding dose escalation only after unblinded review of safety data once all subjects in Cohort 1 reach Week 6 (or prematurely discontinue). Randomization at the higher dose (URO-902 48 mg) will begin only after the DSMB has recommended it is safe to proceed to Cohort 2

- Cohort 1: URO-902 24 mg and matching placebo
- Cohort 2: URO-902 48 mg and matching placebo

An estimated total of 78 subjects will be enrolled into 2 cohorts with approximately 39 subjects randomized into each cohort. In both cohorts, subjects will be randomized in a 2:1 ratio to receive either URO-902 (24 mg or 48 mg) or placebo. Each cohort will be randomized separately, and enrollment will be sequential, starting with Cohort 1 (URO-902 24 mg [n = 26] and placebo [n = 13]) and followed by Cohort 2 (URO-902 48 mg [n = 26] and placebo [n = 13]).

[figure not shown]
Prior to protocol amendment 1, subjects in Cohort 1 were randomized based on two stratification factors: baseline UUI episodes per day (≤ 3 vs. > 3 UUI episodes per day), and presence and absence of detrusor overactivity (DO). Post-protocol amendment 1, subjects were randomized based on a new randomization scheme and presence or absence of DO was replaced with prior onabotulinumtoxinA use. All subjects randomized prior to and post amendment 1 will have the baseline UUI episodes per day as a stratification factor. The subjects randomized under the original randomization scheme will be considered Cohort 1a and subjects randomized under the new randomization scheme will be considered Cohort 1b. For reporting purposes, Cohort 1a and Cohort 1b will be combined and subjects enrolled in Cohort 1a will be considered onabotulinumtoxinA naïve.

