2.3. Data and Safety Monitoring Board

A DSMB will be retained to assess, on an ongoing basis, all safety aspects of this study including unblinded review of safety data after all subjects reach Week 6 (or prematurely discontinue) in Cohort 1 (URO-902 24 mg). Randomization at the higher dose (URO-902 48 mg) will begin only after the DSMB has recommended it is safe to proceed to Cohort 2. This committee will be an external independent DSMB that monitors safety. The detailed activities including meeting plans will be described and documented in the DSMB Charter. A separate statistical analysis plan may be prepared for the DSMB.

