7.2. Adverse Events

Adverse events (AEs) will be coded using MedDRA version 22.1. or later.

All reported AEs (whether treatment emergent or not) will be included in by-subject AE listings. Sorting will be by treatment, subject, date of event, SOC, PT and then verbatim description.

An AE will be considered a treatment emergent adverse event (TEAE) if it begins or worsens in severity after initial exposure of the study treatment through 48 weeks after treatment administration or the date of the initiation of another OAB medication, investigational agent or surgical intervention, whichever occurs first. The determination of "48 weeks" will be based on the study day of the AE start date instead of the visit date of the Week 48 visit. The OAB medication will be determined based on the checkbox "Is this an additional OAB medication"

on the concomitant medication CRF. After data are collected and reviewed by the clinical team, a blinded list of investigational agents and surgical interventions will be provided to the programming team prior to database lock to determine which AEs should no longer be considered treatment emergent due to possible confounding effects. Partial AE start dates will be imputed as detailed in [Section 4.2.3](#).

Summary tables will be based on TEAEs. The incidence of TEAEs will be presented using counts and percentages of subjects with TEAEs and tabulated by SOC and PT. SOC will be sorted in descending frequency and PT within SOC will be sorted by descending frequency based on the incidence of all subjects treated with URO-902 included in the summary. If a subject has multiple occurrences (start and stop) of an event associated with a specific SOC or PT within a SOC, a subject will only be counted once in the incidence count for the SOC or PT within SOC respectively.

An overall summary table of AEs by treatment group will be presented detailing the number and percentage of subjects, and number of events for the following categories:

- At least one TEAE;
- At least one Treatment-Related TEAE;
- At least one Grade ≥ 3 TEAE (Mild = Grade 1, Moderate = Grade 2, Severe = Grade 3, Life-Threatening = Grade 4, Death = Grade 5)
- At least one Grade ≥ 3 Treatment-Related TEAE;
- At least one Serious TEAE;
- At least one Serious Treatment-Related TEAE;
- At least one TEAE leading to Discontinuation from Study;
- At least one TEAE of Special Interest;
- At least one Treatment-Related TEAE of Special Interest

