11. APPENDIX

11.1. Table of Contents for Data Display Specifications

11.1.1. Output Tables

Table 8: List of Output Tables

Title		Population	Programming Note	Deliverable
Study Population				
14.1.1.1	Subject Enrollment	Scanned		EOS
14.1.1.2	Subject Disposition	Randomized		TL, EOS
14.1.1.3	Subject Randomization by Investigator	Randomized		EOS
14.1.2.1	Major Protocol Deviations	Randomized		EOS
14.1.2.2	Reasons for Exclusion from Analysis	Randomized		EOS
14.1.3.1	Demographics and Baseline Characteristics	ITT-E		TL, EOS
14.1.4	Medical History	ITT-E		EOS
14.1.5.1	Prior Medication	ITT-E	ATC Level 2 and 4	EOS
14.1.5.2	Concomitant Medication	ITT-E	ATC Level 2 and 4	EOS
14.1.5.3	Additional OAB Treatment Received Prior to Week 24 (Medication)	ITT-E	ATC Levels 2, 4 and PT	TL, EOS
14.1.5.4	Additional OAB Treatment Received at or After Week 24 (Medication)	ITT-E	ATC Levels 2, 4 and PT	TL, EOS
14.1.5.5	Additional OAB Treatment Received Prior to Week 24 (Procedure)	ITT-E	ATC Levels 2, 4 and PT	EOS

Title		Population	Programming Note	Deliverable
14.1.5.6	Additional OAB Treatment Received at or After Week 24 (Procedure)	ITT-E	ATC Levels 2, 4 and PT	EOS
14.1.6	COVID-19 Impact	ITT-E		EOS
Efficacy Endpoints				EOS
14.2.1.1	Change from Baseline in Average Daily Number of Urge Urinary Incontinence Episodes (MMRM)	ITT-E	Week 12 first, then other visits sequentially	TL, EOS
14.2.1.2	Summary of Average Daily Number of Urge Urinary Incontinence Episodes	ITT-E	By-visit Descriptive Summary	TL, EOS
14.2.1.3	Summary of Average Daily Number of Urge Urinary Incontinence Episodes by Baseline UUI Episodes per Day	ITT-E	Subgroup columns within each treatment arm	EOS
14.2.1.4	Summary of Average Daily Number of Urge Urinary Incontinence Episodes by Presence or absence of DO	ITT-E	Subgroup columns within each treatment arm	EOS
14.2.1.5	Summary of Average Daily Number of Urge Urinary Incontinence Episodes by Previous Use of onabotulinumtoxinA	ITT-E	Subgroup columns within each treatment arm	EOS
14.2.1.6	Change from Baseline in Average Daily Number of Urge Urinary Incontinence Episodes at Week 12	ITT-E		EOS
14.2.1.7	Change from Baseline in Average Daily Number of Urge Urinary Incontinence Episodes (MMRM) - Sensitivity Analysis	ITT-ES	Week 12 first, then other visits sequentially	EOS
14.2.2.1	Change from Baseline in Average Daily Number of Micturitions (MMRM)	ITT-E	Week 12 first, then other visits sequentially	TL, EOS

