14.2.5.2	Summary of Average Volume Voided per Micturition	ITT-E	By-visit Descriptive Summary	TL, EOS
14.2.6.1	Proportion of Subjects Achieving $\geq 50\%$ Reduction in Number of Average Daily Urge Urinary Incontinence Episodes from Baseline	ITT-E	Week 12 first, then other visits sequentially	EOS
14.2.6.2	Proportion of Subjects Achieving $\geq 75\%$ Reduction in Urge Urinary Incontinence Episodes from Baseline	ITT-E	Week 12 first, then other visits sequentially	EOS
14.2.6.3	Proportion of Subjects achieving 100% Reduction in Urge Urinary Incontinence Episodes from Baseline	ITT-E	Week 12 first, then other visits sequentially	TL, EOS
14.2.7.1	Change from Baseline I-QOL Domains (MMRM)	ITT-E	Week 12 first, then Week 6	TL, EOS
14.2.7.2	Summary of I-QOL Scores	ITT-E	By-visit Descriptive Summary	TL, EOS
14.2.7.3	Proportion of Subjects Achieving the Minimally Important Difference in I-QOL Total Summary Score	ITT-E	Week 12 first, then Week 6	EOS
14.2.8.1	Change from Baseline in OAB-q Scores (MMRM)	ITT-E	Week 12 first, then Week 6	TL, EOS
14.2.8.2	Summary of OAB-q Scores	ITT-E	By-visit Descriptive Summary	TL, EOS
14.2.9.1	Change from Baseline on Patient Global Impression Change Score at Week 12	ITT-E	Week 12 only	TL, EOS
14.2.9.2	Summary of Patient Global Impression	ITT-E	By-visit Descriptive summary and change from baseline of numeric score	EOS
14.2.10	Summary of Urodynamic Parameters	ITT-E	Baseline and Week 12 only	EOS
14.2.11	Summary of hSlo cDNA Concentrations	ITT-E		TL, EOS
14.2.12.1	Change from Baseline in Average Daily Number of Nighttime Voids (MMRM)	ITT-E	Week 12 first, then other visits sequentially	EOS

Title		Population	Programming Note	Deliverable
14.2.12.2	Summary of Average Daily Number of Nighttime Voids	ITT-E	By-visit Descriptive Summary	EOS
14.2.13.1	Proportion of Subjects Achieving $\geq 50\%$ Reduction in Number of Average Daily Urinary Incontinence Episodes from Baseline	ITT-E	Week 12 first, then other visits sequentially	EOS
14.2.13.2	Proportion of Subjects Achieving $\geq 75\%$ Reduction in Number of Average Daily Urinary Incontinence Episodes from Baseline	ITT-E	Week 12 first, then other visits sequentially	EOS
14.2.13.3	Proportion of Subjects Achieving 100% Reduction in Number of Average Daily Urinary Incontinence Episodes from Baseline	ITT-E	Week 12 first, then other visits sequentially	EOS
Safety Endpoints				
Adverse Events				
14.3.1.1	Overall Treatment-Emergent Adverse Events	Safety		TL, EOS

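### TEAE tables run at a planned interim would give the 24 mg arm longer time at risk than the later-enrolled 48 mg arm, because the SAP states no common per-subject cut-off

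*SAP*

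**What the plan says.** **Timing of the interims.** SAP 2.1 triggers the first planned interim when "All subjects in Cohorts 1 and 2 have completed Week 12 (or prematurely exited the study prior to Week 12" and adds that "a second planned interim analysis will be conducted after all subjects complete Week 24 (or prematurely exited the study prior to Week 24". It says these evaluate the protocol objectives at Week 12 and at Week 24, and that any interim is for future planning. It gives no per-subject data cut.

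**Order of the cohorts.** SAP 1.2.1: "Each cohort will be randomized separately, and enrollment will be sequential", with 24 mg first. SAP 2.3 requires "unblinded review of safety data after all subjects reach Week 6 (or prematurely discontinue) in Cohort 1" and a favourable DSMB recommendation before anyone is randomized to 48 mg.

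**Event window and measure.** Under SAP 7.2 an event counts if it starts or worsens after dosing "through 48 weeks after treatment administration or the date of the initiation of another OAB medication, investigational agent or surgical intervention, whichever occurs first". Results are counts and percentages of subjects. SAP 7.1 plans no exposure summary, and the list of tables contains no summary of follow-up time.

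**Tables.** In SAP 11.1.1, Table 14.3.1.1 ("Overall Treatment-Emergent Adverse Events") is marked for both topline (TL) and end of study (EOS). So are Tables 14.3.1.2.1, 14.3.1.3.1, 14.3.1.7 (serious), 14.3.1.10 (leading to discontinuation) and 14.3.7 (PVR). The TEAE tables split at Week 24 are EOS only. SAP 7.7 derives maximum and last PVR from any post-baseline value, outside the visit windows.

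**The concern.** The efficacy tables are organised by visit, so the two doses are compared at the same time after treatment. The TEAE tables have no such anchor before the end of the study. At an interim triggered by the last subject, a subject contributes whatever follow-up she has, up to 48 weeks. Dose and follow-up time are tied together because 24 mg was enrolled first.

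A crude percentage rises with time at risk. If the true risks are equal, 48 mg is then expected to show fewer TEAEs than 24 mg, and a real dose-related excess could be partly or wholly masked. The SAP says interim output serves future planning, and the safety of the two doses is among the protocol objectives, so this comparison may well be used.

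**Working it through.** The plan gives no follow-up time or event rate by arm, so it has no figure to reproduce here.

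**Inputs from the documents.** 48-week window (SAP 7.2); triggers at the last subject's Week 12 and Week 24 (SAP 2.1); Cohort 2 gated on the last Cohort 1 subject's Week 6 (SAP 2.3); 26 subjects per dose arm (SAP 1.2.4). Visit days are nominal and early exits are ignored.

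**Assumptions, not in the documents.** Uniform accrual over E1 = 12 to 36 weeks (Cohort 1) and E2 = 12 to 48 weeks (Cohort 2); DSMB review L = 2 to 4 weeks; true 48-week TEAE risk of 40% in both arms.

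**Step 1: follow-up at the Week 12 trigger.** Counting from the first Cohort 1 dose, Cohort 2 starts at E1 + 6 + L and the trigger falls at E1 + 6 + L + E2 + 12.
- Every retained 24 mg subject has at least 6 + L + E2 + 12 = 18 + L + E2 weeks, up to the 48-week cap. The last 48 mg subject has 12.
- Before the cap, the mean gap is 6 + L + (E1 + E2)/2.
- With instant accrual and review: 18 versus 12 weeks, a gap of 6.
- The cap narrows the gap when accrual is long. Once all 24 mg subjects have reached 48 weeks and E2 is at least 36, the gap is 36²/(2 × E2) = 648/E2. That drops below 6 only if E2 exceeds 108 weeks.

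**Step 2: worked case**, E1 = E2 = 12, L = 2. Cohort 2 is dosed in Weeks 20 to 32 and the trigger is Week 44. Follow-up is 32 to 44 weeks for 24 mg (mean 38) and 12 to 24 for 48 mg (mean 18). The gap is 20, matching 6 + 2 + 12.

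**Step 3: expected crude incidence.** The total hazard is −ln(0.6) = 0.511. Incidence at follow-up t is 1 − exp(−0.511 × g(t)), where g(t) is the share of hazard accrued, averaged over subjects.
- Constant hazard, g = t/48: 33.2% versus 17.4%, about 16 points.
- Half the hazard in the first 2 weeks, g = 0.5 + 0.5(t − 2)/46: 36.6% versus 29.1%, about 7 points.

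**Step 4: range over the assumed accrual and review times**

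| Trigger | Mean gap (weeks) | Constant hazard (points) | Half in first 2 weeks (points) |
|---|---|---|---|
| Week 12 | 13.5 to 27.3 | 9.8 to 20.8 | 4.8 to 10.0 |
| Week 24 | 6.0 to 17.9 | 4.2 to 12.7 | 2.1 to 6.3 |

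Ends of the Week 12 gap:
- E2 = 48 gives 648/48 = 13.5.
- E1 = 36, E2 = 12, L = 4 gives a 24 mg mean of (22 × 48 + 14 × 41)/36 = 45.3, against 18 for 48 mg, a gap of 27.3.

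In a 26-subject arm, 10 to 21 points is about 2.6 to 5.5 subjects, and 5 to 10 points is about 1.3 to 2.6.

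**Step 5: what shrinks it**
- *Additional OAB medication.* This ends the TEAE window. In the limiting case where every subject starts it at Week 24, capping follow-up at 24 weeks cuts the Week 12 gap to 1.5 to 6.0 weeks and the Week 24 gap to zero.
- *Stronger front-loading.* With 80% of the hazard spread over Weeks 0 to 6 and the rest over Weeks 6 to 48, the Week 12 difference is about 2 to 4 points.

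**Step 6: after a common 12-week cut.** Both arms have t = 12, so equal risks give equal expected incidence: 12.0% in each under the constant hazard.

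**The case against.** Several limits are fair.

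- **TL is not tied to an interim.** The SAP expands it only as topline. A reader might infer that the topline TEAE tables are cut at the last subject's Week 12; the documents do not say so. Table 14.1.5.4 ("Additional OAB Treatment Received at or After Week 24 (Medication") is also TL. That suggests later data are kept, but it fits a Week 24 topline just as well. The imbalance arises at either interim.
- **A cut may be intended.** SAP 2.1 speaks of objectives at Week 12 and at Week 24, and layouts sit in a separate programming document. But SAP 7.2 defines one TEAE window with no interim variant, so a programmer following the SAP would apply 48 weeks.
- **Placebo.** A reader might infer that 48 mg would also look better than placebo. SAP 1.2.3 states pooling across cohorts only for the final analysis, and SAP 4.2.1 provides for reporting within a cohort. Against concurrent placebo, planned follow-up is balanced by randomization. Only pooling at the interim would carry the problem over; in the worked case, pooled placebo would have (38 + 18)/2 = 28 weeks.
- **PVR.** By-visit summaries are aligned by study day. Only maximum and last values are exposed, mainly at the Week 12 interim, since the last scheduled PVR is at Week 24.
- **Size.** Accrual, review time, risk and hazard shape are all assumed. Events after a single injection procedure may cluster early, and OAB medication shortens mainly the 24 mg window.
- **Reach.** SAP 2.2 bases the study report on the final analysis, when every arm has a nominal 48 weeks, and ongoing safety oversight rests with the DSMB.

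These points limit the size and reach of the problem. They do not remove the direction of the bias in the interim dose comparison.

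**Conclusion.** The concern holds conditionally. If the TEAE tables and the maximum and last PVR are produced at the planned Week 12 or Week 24 interim under the stated rules, 24 mg has longer time at risk than 48 mg, and equal true risks are expected to give a lower crude TEAE percentage at 48 mg. The direction follows from the SAP itself, leaving aside early exits, visit windows and closure of the TEAE window by OAB medication.

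Only the 6-week floor at the Week 12 trigger needs no accrual assumption beyond Cohort 2 enrolling within 108 weeks. The 13 to 27 week gap, and the 10 to 21 or 5 to 10 point differences, rest on the assumed accrual, review time, 40% risk and hazard shape. They are smaller with stronger front-loading or wide use of OAB medication from Week 24.

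The documents do not support reading this as a bias in the final analysis, in the study report, in by-visit PVR or in comparisons with concurrent placebo. It should be corrected before interim output is used to compare the doses.

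**What to change.** In SAP 2.1 and 7:

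1. State which planned interim the TL tables belong to.
2. For each planned interim, let the between-dose tables of TEAEs, serious TEAEs, TEAEs leading to discontinuation, and maximum and last PVR count only data up to a common study day per subject: the end of the Week 12 window for the first and of the Week 24 window for the second. Keep the 48-week window for the EOS tables.
3. Put later events in a separate by-cohort table and in the listings.
4. Add a summary of follow-up time by arm.
5. Compare each dose with its concurrent placebo, or with pooled placebo under the same cut.

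The cost is a few SAP sentences, a study-day filter in the interim programs and two short tables. The downside is that later Cohort 1 events leave the main interim table, though they stay visible in the separate table and listings. Exposure-adjusted rates could supplement the cut, but they remove the imbalance only if the hazard is roughly constant.
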